10.10.3. Substudy Objectives and Endpoints

10.10.4. Substudy Design

This is a substudy of the main B7451094 open label parallel group study. This substudy is being performed to evaluate whether abrocitinib has any potential effects on adolescent bone with regard to bone safety findings in knee MRI, including to assess if there is any abrocitinib associated effects on cartilage mineralization in the actively growing bones of adolescent participants with moderate to severe AD in India, and to verify that epiphyseal plate closure occurs as expected in late adolescence or early adulthood. All adolescent participants who were 12 to <18 years of age at the screening visit will be enrolled in this substudy. This substudy will continue until 1 year after all enrolled adolescent participants in the main study have been randomized to study intervention.

Prior to knee MRI at the screening visit of the main study, informed consent and assent (if applicable) will be obtained. Adolescent participants will continue to receive the assigned abrocitinib 100 mg or 200 mg QD after the 12-week treatment period in the main study, until 1 year after the participant was randomized in the main study, when a second MRI imaging will be performed at the substudy end of treatment visit. Both imaging sessions will require participants to be in a supine position in the confined space of the MRI scanner for approximately 30 minutes.

The same knee for each participant will be evaluated in the substudy. The default knee selected to be evaluated will be the participant's left knee. The right knee will only be selected and used if there is a prior history of significant trauma or abnormality of the left knee, such as any knee condition requiring surgery, any knee condition that is a birth defect, or any condition which has resulted in long-term (>6 months) knee pain, reduction in knee function, or abnormal gait (Note: This is not an all-inclusive list), or any other reason that the left knee is unsuitable for MRI in the Investigator's judgement.

MRIs will be evaluated by a central reader, and reviewers will be radiologists; who are experienced in pediatric imaging and proficient in the interpretation of pediatric bone imaging. The assessments will include evaluation of epiphyseal plate closure and mineralization of cartilage at the growth centers. The radiologist(s) will evaluate the images using a standardized case report form. If any bone safety finding(s) are determined to be present in the central evaluation of the post-dose knee MRI images at the substudy end of treatment visit or early termination visit, then the adjudication committee will adjudicate the diagnosis as per the adjudication charter. The Investigator will determine based on the MRI central read and (if relevant) any suggested further assessment/investigation made by the adjudication committee, and (if relevant) the adjudication outcome if any further follow-up or investigation is required. The Investigator will be responsible for recording any medical

history or AEs that they determine. The Investigator holds responsibility for reviewing all MRI central read reports and adjudication outcomes, and performing a general safety review based on these.

The participants of this substudy will complete all other protocol-specific procedures in the main study.

Adolescent participants who discontinue from the main study will also be discontinued from the substudy. For participants that withdraw during the main study period, an end of treatment/early termination knee MRI for the participant should be performed approximately within 1 month of the main study end of treatment/early termination visit, and then the participant should enter into the follow-up period, with a main study end-of-study visit scheduled for 4 weeks after the end of treatment visit MRI.

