10.10.5.1. Substudy Inclusion Criteria

Participant must meet all of the following inclusion criteria to be eligible for enrollment into the substudy:

- 1. 12 to <18 years of age, at the time of screening visit;
- 2. Evidence of a personally signed and dated informed consent document, and/or informed consent of the legally authorized representative (parent/guardian), and assent of the study participant, indicating that the participant or their parent(s)/legal guardian, if applicable, have been informed of all pertinent aspects of the substudy;
- 3. At least one knee suitable for MRI in the Investigator's judgment, without prior history of significant trauma or abnormality eg, any knee condition requiring surgery, any knee condition that is a birth defect, or any condition which has resulted in long-term (>6 months) knee pain, reduction in knee function, or abnormal gait (Note: This is not an all -inclusive list);
- 4. Willing and able to comply with substudy scheduled visits and subsstudy procedures including knee MRI imaging.

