10.10.5.2. Substudy Exclusion Criteria

Participant with any of the following characteristics/conditions will not be included in the study:

1. Participant who has any absolute or relative contraindication for an MRI scan, such as implants, metallic foreign bodies, claustrophobia. (Note: This is not an all inclusive list).

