10.10.6. Substudy Study Treatments

There are no additional requirements for the substudy and the requirements from the main study apply, except that adolescent participants who enter the substudy will continue to receive study intervention as assigned in the main study after the 12-week treatment period, until 1 year after randomization in the main study or until they turn 18 years of age. Participants will be dispensed bottles of study intervention at Week 12, Week 24 and Week 36 visits. Please refer to the Study Intervention(s) and Concomitant Therapy section (Section 6) of the main protocol for further details.

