10.10.7.4. Substudy Discontinuation Criteria

A participant will be discontinued from the substudy and have a Substudy Early

Termination/End of Treatment Visit if:

- The participant meets any of the discontinuation criteria of the main B7451094 study;
- If the participant is no longer an active participant of the main B7451094 study;
- If the participant has turned 18 years of age during the substudy.

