## PFIZER GENERAL BUSINESS

• The incidence rate of bone safety findings in knee MRI, along with the 95% CI will be estimated for baseline and End of Treatment (EOT) in the substudy, for each treatment arm. In addition, the types of bone safety findings will be summarized.

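### The knee-MRI substudy aims to verify growth-plate closure and to detect effects in growing bone, but the SAP plans no summary of plate status and pools its bone-finding rate over participants whose plates may already be closed

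*Protocol*

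**What the plan says.** **Aims.** Protocol 10.10.1.1 and 10.10.4 give two specific purposes within the general bone-safety question. One is to look for "effects on cartilage mineralization in the actively growing bones of adolescent participants". The other is "to verify that epiphyseal plate closure occurs as expected in late adolescence or early adulthood".

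**Eligibility.** Protocol 10.10.5.1 asks for "12 to <18 years of age, at the time of screening visit", consent and assent, a knee suitable for MRI, and willingness to comply. The single exclusion in 10.10.5.2 begins "Participant who has any absolute or relative contraindication for an MRI scan". Neither list mentions an open plate or skeletal maturity.

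**Follow-up.** Under protocol 10.10.6 treatment runs "until 1 year after randomization in the main study or until they turn 18 years of age". A discontinuation criterion in 10.10.7.4 reads "If the participant has turned 18 years of age during the substudy". Protocol 10.10.7.2 places the MRI for these participants shortly after the birthday. Footnote c of the substudy schedule (10.10.2) says that those who turn 18 during the main study have a baseline MRI only.

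**Reading.** Protocol 10.10.4 states: "The assessments will include evaluation of epiphyseal plate closure and mineralization of cartilage at the growth centers". A standardized form is used, and MRIs are scheduled at screening and at early termination/end of treatment (ET/EOT).

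**Analysis.** SAP 2.1.3 divides participants with bone safety findings by all who received treatment during the substudy, per arm. SAP 6.3.1 gives that rate with a 95% CI at baseline and EOT, and adds: "In addition, the types of bone safety findings will be summarized". Appendix 1 of the SAP lists nothing further for MRI. The only subset analysis (SAP 6.4) concerns efficacy by monotherapy or combination therapy.

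**The concern.** Closure is a normal event in this age range, and both arms receive abrocitinib. A pooled proportion of bone safety findings therefore cannot show how many plates were open at the start, how many closed on study, or at what ages. The aim of verifying closure has no planned output, although the data for a description are read.

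The denominator raises a second issue. The protocol itself expects closure to begin in the late teens, so some entrants may already be closed at baseline. They are not at risk of an effect that needs an open plate, yet each counts fully in the rate. A low pooled rate could then be taken as firmer reassurance about growing bone than the data at risk support.

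**Working it through.** **1. The plan's own precision figure.** The substudy states no sample size, expected rate or precision (protocol 10.10.10.1). The only figure is for the main study (9.5): 100 per arm, maximum margin of error 10%. Check: 1.96 × √(0.5 × 0.5 / 100) = 9.8%, which agrees. It does not carry over to an adolescent subset of unknown size.

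**2. Aim against output.**

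| Element | Planned? | Where |
|---|---|---|
| Plate closure evaluated by central reader | Yes | Protocol 10.10.4 |
| Incidence and types of bone safety findings per arm | Yes | SAP 6.3.1 |
| Plate status at baseline or EOT | No | – |
| Change in plate status | No | – |
| Bone findings by plate status, age or sex | No | – |

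**3. Ages observed.** The documents give no age distribution. Assume, for illustration, that entry ages are uniform over 12 to <18, a span of 6 years:

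- turn 18 within one year: 1/6 = 16.7%;
- of all adolescents, turn 18 in the first 12 weeks (baseline MRI only): (84/365.25)/6 = 3.8%;
- turn 18 later in the year (scanned just after 18): (1 − 84/365.25)/6 = 12.8%;
- finish at one year while still under 18: 5/6 = 83.3%.

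On this assumption, observation of adulthood is confined to scans soon after the 18th birthday in roughly one participant in eight.

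**4. Effect on the pooled rate.** Let p be the true incidence among open-plate participants and c the share closed at baseline. If a finding can arise only at an open plate, the pooled rate estimates p × (1 − c). With an assumed p = 10% it is 9.0%, 8.0% or 7.0% for c = 10%, 20% or 30%.

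**5. Effect on apparent precision.** With 0 findings in n, the exact (Clopper-Pearson) 95% upper limit is 1 − 0.025^(1/n). This is the SAP's own method for an estimated proportion of 0 (SAP 5.2.1). Both the number per arm and c are assumptions.

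| Assumed per arm | All treated | 10% closed | 20% closed | 30% closed |
|---|---|---|---|---|
| 30 | 11.6% | 12.8% (n=27) | 14.2% (n=24) | 16.1% (n=21) |
| 20 | 16.8% | 18.5% (n=18) | 20.6% (n=16) | 23.2% (n=14) |

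Example: 1 − 0.025^(1/30) = 11.6%; 1 − 0.025^(1/24) = 14.2%.

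**The case against.** The strongest reply is that the formal objective, endpoint and analysis agree with one another: bone development in participants aged 12 to <18, measured by bone safety findings. Plate closure appears as an inclusive clause in the rationale and design text, without an endpoint of its own, and enrolling older adolescents is consistent with wanting to see closure. Findings are defined in the image review and adjudication charters, which are not among the documents. If abnormal closure is a defined finding, it would enter the incidence and the summary of types. This stands as far as it goes. Even so, there would be no count of plates at risk and no description of ordinary closure, so the stated aim would still lack an output.

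Four stronger readings are tempting, and the documents do not support them:

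- *Everyone is stopped at 18.* The age rule affects only those who reach 18 on study; the others stop at one year.
- *Adulthood is never imaged.* Participants who turn 18 after the main study are scanned just after the birthday (protocol 10.10.7.2).
- *Closure is not assessed.* It is read centrally; only the analysis is missing.
- *The bone rate is too low by some known amount, perhaps as much as half.* No closed share is documented. A large share would also sit awkwardly with an age range in which, under uniform entry, 17-year-olds are about one sixth. The formula in step 4 further requires that findings occur only at open plates, whereas the endpoint covers bone safety findings generally.

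A fair criticism of the obvious remedy also stands. A table by sex and single year of age has 2 × 6 = 12 cells per arm, or about 2 participants per cell at 20 to 30 per arm. Without an untreated control it could not establish that closure was on time.

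**Conclusion.** The point holds as a gap between stated aim and planned analysis. Carried out exactly, the plan says nothing about plate status or its change, and early adulthood is essentially outside the observation period. This follows from the text and needs no assumption.

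The effect on the bone-finding rate is conditional. Its direction is clear for findings that need an open plate, provided at least one participant is closed at baseline: the pooled rate is lower, and its interval narrower, than for the growing skeleton. Its size cannot be derived; the figures in steps 4 and 5 illustrate it under assumed inputs.

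The primary substudy endpoint is not invalidated. This is an inexpensive improvement to analysis and wording, and it lets the substudy address its own question more directly.

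**What to change.** In SAP 6.3.1 and protocol 10.10.10.3:

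1. Tabulate plate status (open, partly closed, closed) from baseline to ET/EOT MRI by arm, with sex and broad age bands, or as a listing. Avoid single years of age.
2. Beside the all-treated rate, report bone-finding incidence with an exact CI in participants who had an open plate at baseline and have a post-dose MRI. Baseline status comes from a pre-dose scan, so treatment cannot affect it. Show how many open-plate participants lack a post-dose MRI.
3. In protocol 10.10.1.1 and 10.10.4, limit the aim, and later the conclusion, to descriptive change in plate status over up to one year, to about age 18, without an untreated control.

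Separately, protocol 4.1 and 10.10.4 describe one year of treatment for all adolescents, while 10.10.6, 10.10.7.2 and 10.10.7.4 add an end at age 18. These passages must be reconciled; this review takes no position on which rule should apply.

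Cost: wording and two outputs from readings already planned, with no extra scans or participants. The downside is a smaller denominator and a wider, less favourable interval for the open-plate rate.

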10.10.5. Substudy Eligibility Criteria

This substudy can fulfill its objectives only if appropriate participants are enrolled. The following eligibility criteria are designed to select participants for whom participation in the substudy is considered appropriate. All relevant medical and nonmedical conditions should be taken into consideration when deciding whether a particular participant is suitable for this substudy.

Participant eligibility should be reviewed and documented by an appropriate member of the Investigator's study team before participants are included in the substudy.

10.10.5.1. Substudy Inclusion Criteria

Participant must meet all of the following inclusion criteria to be eligible for enrollment into the substudy:

- 1. 12 to <18 years of age, at the time of screening visit;
- 2. Evidence of a personally signed and dated informed consent document, and/or informed consent of the legally authorized representative (parent/guardian), and assent of the study participant, indicating that the participant or their parent(s)/legal guardian, if applicable, have been informed of all pertinent aspects of the substudy;
- 3. At least one knee suitable for MRI in the Investigator's judgment, without prior history of significant trauma or abnormality eg, any knee condition requiring surgery, any knee condition that is a birth defect, or any condition which has resulted in long-term (>6 months) knee pain, reduction in knee function, or abnormal gait (Note: This is not an all -inclusive list);
- 4. Willing and able to comply with substudy scheduled visits and subsstudy procedures including knee MRI imaging.

10.10.5.2. Substudy Exclusion Criteria

Participant with any of the following characteristics/conditions will not be included in the study:

1. Participant who has any absolute or relative contraindication for an MRI scan, such as implants, metallic foreign bodies, claustrophobia. (Note: This is not an all inclusive list).

10.10.5.3. Substudy Enrollment Criteria

Participants will be enrolled into the substudy provided they have an appropriately signed informed consent document and have evidence of assent, if applicable (ie, current minors), to participate in the substudy, and meet all inclusion and none of the exclusion criteria for participation in the substudy at the screening/enrollment visit.

10.10.5.4. Substudy Lifestyle Requirements

There are no additional requirements for the substudy. The requirements from the main protocol apply. Please refer to the Lifestyle Considerations section (Section 5.3) of the main protocol for further details.

10.10.6. Substudy Study Treatments

There are no additional requirements for the substudy and the requirements from the main study apply, except that adolescent participants who enter the substudy will continue to receive study intervention as assigned in the main study after the 12-week treatment period, until 1 year after randomization in the main study or until they turn 18 years of age. Participants will be dispensed bottles of study intervention at Week 12, Week 24 and Week 36 visits. Please refer to the Study Intervention(s) and Concomitant Therapy section (Section 6) of the main protocol for further details.

10.10.7. Substudy Study Procedures

The study procedures for the substudy are described below.

If for whatever unanticipated reason a participant is unable to attend the site visit, the substudy procedures may be performed remotely where locally permissible and where an acceptable and feasible approach has been agreed with the study team and/or detailed per protocol.

10.10.7.2. Substudy Early Termination/End of Treatment Visit

• A Substudy End/Early Termination Visit will be performed approximately within 1 month of the participant turning 18 years of age, OR whenever the participant discontinues from the substudy, OR 1 year after participant randomization in the main study; whichever is the sooner.

• An MRI should be arranged approximately within 1 month of the visit (but must be AFTER the participant has turned 18 years of age if participant is completing substudy due to turning 18).

- After the MRI is performed, review if any abnormal knee MRI findings then:
 - Review findings identified by central reader MRI evaluation, and (if relevant) the adjudication report, and arrange any further follow-up and investigation, if relevant and required;
 - Record medical history/adverse event/laboratory assessment abnormality as appropriate.

10.10.7.3. Substudy Follow-up Visit

- MRI may be required if any clinically significant finding is identified in knee MRI following the substudy early termination/end of treatment visit or if for any reason MRI was not performed following the end of treatment visit. This MRI, if required, must be performed **prior** to the substudy follow up visit. After the MRI is performed, review if any abnormal knee MRI findings then:
 - Review findings identified by central reader MRI evaluation, and (if relevant) the adjudication report, and arrange any further follow-up and investigation, if relevant and required;
 - Record medical history/adverse event as appropriate.

Note: if any participant requires MRI following the end of treatment visit, the expectation is that the MRI would be arranged as soon as feasible and that the substudy follow up visit be conducted as close to the stated visit window as possible. It will not be considered a protocol deviation as long as the substudy follow up visit occurs no more than 14 days after the completion of the MRI in such cases.

10.10.7.4. Substudy Discontinuation Criteria

A participant will be discontinued from the substudy and have a Substudy Early

Termination/End of Treatment Visit if:

- The participant meets any of the discontinuation criteria of the main B7451094 study;
- If the participant is no longer an active participant of the main B7451094 study;
- If the participant has turned 18 years of age during the substudy.

10.10.7.5. Substudy Participant Withdrawal

Participants may withdraw from the substudy at any time and for any reason. Participants will be withdrawn from the substudy if they are no longer an active participant of the main study. The requirements and discontinuation criteria from the main protocol apply for the substudy. Please refer to Participant Withdrawal section (Section 7.2) of the main protocol for further details.

10.10.8. Substudy Assessments

Every effort should be made to ensure that the protocol-required tests and procedures are completed as described. However, it is anticipated that from time to time there may be circumstances outside of the control of the Investigator that may make it unfeasible to perform the test. In these cases, the Investigator will take all steps necessary to ensure the safety and well-being of the participant. When a protocol-required test cannot be performed, the Investigator will document the reason for this and any corrective and preventive actions that he or she has taken to ensure that normal processes are adhered to as soon as possible. The study team will be informed of these incidents in a timely manner.

PFIZER CONFIDENTIAL

Page 106

10.10.8.1. Bone Safety Findings Identified in Central Evaluation of Knee MRI Images

All bone safety findings will be recorded in the CRF as either medical history or treatment emergent adverse events, as determined by the Investigator.

If any bone safety finding(s) are determined to be present in the central evaluation of the postdose knee MRI images, then the adjudication committee will adjudicate the diagnosis as per the adjudication charter.. The adjudication committee may suggest further follow up or investigation for Investigator consideration. The Investigator will receive a report of the MRI central read and the adjudication outcome, and will determine if any further follow-up or investigation is required.

The Investigator will ensure the recording of any AEs as described in the Adverse Event Reporting section (Section 8.3 and Section 10.10.9), or medical history, if relevant.

If any potential bone safety findings, as per the image review charter, are determined to be present in the MRI central read report, then these findings are to be reported to Pfizer Safety as an important medical event on the CT SAE form within 24 hours of awareness of the event. These potential bone related safety findings are to initially be detailed as potentially related to study intervention under study. If subsequently determined (e.g. following further history, examination, investigation, adjudication) that the finding is unrelated to study intervention, then this must be updated by submitting a follow up CT SAE form within 24 hours of awareness.

Incidental/Unrelated Findings:

An incidental finding is one unknown to the participant and has potential health or reproductive importance, which is discovered unexpectedly in the course of a research study, but is unrelated to the purpose and beyond the aims of the study.

MRI images will be reviewed by a central review facility. The purpose of this review will be to further evaluate whether abrocitinib has any potential effects on adolescent bone with regard to abnormal finding(s) in knee MRI, *but* are not a complete medical review of the participant. If during the central review process, any other unexpected observation is identified and this finding could, in the opinion of the central reviewer, have a significant health or reproductive consequence, this finding will be shared on the central read report to the Investigator. All follow-up testing and final diagnosis will be left to the discretion of the medical professionals at the site or those with an existing physician-patient relationship. Identification of such incidental findings during the central review process should not be expected, and the site maintains responsibility for performing a general safety review of all images as per site protocols.

Related Findings:

A related finding is one that is judged by the Investigator to be possibly related to study intervention.

The Investigator will make a judgment regarding the underlying cause of all treatment emergent AEs. If necessary/required, the Investigator may discuss further with orthopedic specialist(s) or other relevant specialist(s) to help inform this judgement, but the judgement will ultimately be made by the Investigator.

